1.3 Correlative Studies

With exception of the peripheral blood sample collected on Cycle 1 Day 4, all correlative studies will be collected under HRPO# 201011766 (“Tissue Acquisition for Analysis of Genetic Progression Factors in Hematologic Diseases”) that all patients will be concurrently enrolled in. The goals of the correlative studies include:

1. To correlate patient-specific mutations with response to decitabine.
We will perform exome sequencing of each patient’s pre-study bone marrow sample and skin sample. We will determine AML/MDS-associated variants found in the bone marrow, but not skin sample. We will correlate the presence of mutations with response (especially mutations in *DNMT3A*, *IDH1*, *IDH2*, and *TET2*). This study is powered to identify mutations with >80% sensitivity to predict decitabine response if used as a clinical assay.
2. To correlate the velocity and depth of response with response to decitabine.
We will assess tumor burden by allele frequency of patient-specific mutations in bone marrow samples collected pre study, Cycle 1 Day 10±1, Cycle 1 Day 28±4, and Cycle 2 Day 28±4. We will assess mutations in at least 24 recurrently mutated genes (including, but not limited to: *FLT3*, *DNMT3A*, *NPM1*, *TET2*, *WT1*, *IDH1*, *IDH2*, *RUNX1*, *NRAS*, *TP53*, *U2AF1*, *KRAS*, *PHF6*, *MSTP9*, *PTPN11*, *KIT*, *SMC3*, *PRUNE2*, *ETV6*, *CEBPA*, *SMC1A*, *ASXL1*, *STAG2*, *RAD21*) as well as all patient-

specific mutations discovered during exome sequencing. The leukemic allele frequency will be measured using the Illumina MySeq or HiSeq platform using DNA capture by gene specific biotinylated-oligonucleotides. Patient bone marrow samples will be assessed pre-study, Cycle 1 Day 10 \pm 1, Cycle 1 Day 28 \pm 4, and Cycle 2 Day 28 \pm 4 and compared with patient specific skin samples (normal control). The velocity of response will be calculated as the natural log rate of patient-specific mutation allele frequency clearance. Depth of response will be defined as the lowest patient-specific mutation allele frequency in a bone marrow sample. The velocity and depth of tumor response will be correlated to:

- Achievement of clinical CR,
- Time to best response,
- Mutational status,
- Time to disease progression.

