A power analysis was performed using Chi-square test for the association between mutation and response to decitabine. The frequency of *DNMT3A*, *IDH1/2*, and *TET2* mutations in AML and MDS patients are each between 15% and 30% in multiple cohorts.[29-37] **Table 3** shows the minimal detectable differences of response rates between mutant and wild-type cases, assuming an expected overall 45% CR/CRi rate and 80% power. For an average of 20% frequency of a mutated gene, for example, 100 patients will provide 80% power to detect 30% difference at a 2-sided 0.1 alpha error. The purpose of this study is to determine whether any of these mutations result in a clinically significant association that would warrant pre-treatment testing. We believe that a reasonable cut off would be if at least 30% of clinical response could be attributed to the presence of a specific mutation. However, we anticipate that more power could be achieved as we assess patient groups with combined characteristics (e.g. *DNMT3A* mutation or loss of *DNMT3A* expression). In addition, we

Table 3. Detectable mutation associated response rates (80% power, $\alpha = 0.05$)

Total N	% of patients with a given mutation	Detectable response difference	Sensitivity of mutation to predict response at minimum detectable response difference*
100	15%	0.40	80%
	20%	0.35	75%
	30%	0.30	67%
	40%	0.27	61%
	50%	0.26	58%

* Assuming the overall response rate (CR/CRi) of 45%

expect that the majority of the enrolled 125 patients can be used in the analysis (since all of our molecular information will be acquired within 30 days of enrollment, we anticipate a drop-out rate of 20% or less).

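### Table 3 labels the response rate in mutation carriers (PPV) as sensitivity, so the Section 1.3 claim of more than 80% sensitivity is unsupported and cannot hold for any single named gene

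*Combined protocol and SAP*

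**What the plan says.** Section 14.2.2 describes the basis of the design: "A power analysis was performed using Chi-square test for the association between mutation and response to decitabine". Table 3 takes 100 patients, 80% power and alpha 0.05. It lists the detectable difference in response rate between mutated and unmutated patients as 0.40, 0.35, 0.30, 0.27 and 0.26 for mutation frequencies of 15, 20, 30, 40 and 50%. Its last column is headed "Sensitivity of mutation to predict response at minimum detectable response difference" and runs 80, 75, 67, 61, 58%. The footnote gives the remaining input: "Assuming the overall response rate (CR/CRi) of 45" percent. The same section puts the frequencies of DNMT3A, IDH1/2 and TET2 mutations at 15 to 30% each, and says the aim is to find associations strong enough to justify testing before treatment.

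Section 1.3 draws the headline from this: "This study is powered to identify mutations with >80% sensitivity to predict decitabine response if used as a clinical assay".

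**The concern.** Sensitivity and PPV condition in opposite directions. Sensitivity asks what share of responders carry the mutation; PPV asks what share of carriers respond. With the difference and overall rate fixed as in Table 3, sensitivity should rise with mutation frequency, because a common mutation can account for more of the responders. The printed column falls, as PPV does.

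The distinction matters for the stated purpose. A reader deciding whether a gene merits pre-treatment testing would take 80% sensitivity to mean that a negative result nearly rules out response. If the figure is PPV, a negative result says much less, and most responders may be unmutated.

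**Working it through.** **Inputs, all from Section 14.2.2 and Table 3.** Overall response 0.45; mutation frequency f; detectable difference d (mutated minus unmutated).

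**Formulas.**
- Response in carriers: p_c = 0.45 + (1 − f)d. This is PPV.
- Response in non-carriers: p_n = 0.45 − f·d.
- Sensitivity: f·p_c / 0.45.
- Ceiling on sensitivity, if every carrier responded: f / 0.45, capped at 1.

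**Step 1: reproduce the printed column.** For the first row, p_c = 0.45 + 0.85 × 0.40 = 0.79 and p_n = 0.45 − 0.15 × 0.40 = 0.39. Sensitivity is 0.15 × 0.79 / 0.45 = 0.263. All rows:

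| f | d | Printed column | p_c (PPV) | p_n | Sensitivity | Ceiling |
|---|---|---|---|---|---|---|
| 15% | 0.40 | 80% | 79.0% | 39.0% | 26.3% | 33% |
| 20% | 0.35 | 75% | 73.0% | 38.0% | 32.4% | 44% |
| 30% | 0.30 | 67% | 66.0% | 36.0% | 44.0% | 67% |
| 40% | 0.27 | 61% | 61.2% | 34.2% | 54.4% | 89% |
| 50% | 0.26 | 58% | 58.0% | 32.0% | 64.4% | 100% |

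PPV reproduces every row within 2 points. The 15, 20 and 30% rows are printed 1 to 2 points high, so the match is close but not exact. Sensitivity reproduces no row.

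**Step 2: try other measures.** None fits the whole column:
- Specificity: 94, 90, 82, 72, 62%.
- Negative predictive value: 61, 62, 64, 66, 68%.
- If the mutation lowers response and its absence is the positive test, sensitivity is 96, 92, 84, 74, 64%.

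**Step 3: check that the small mismatch is harmless.** Taking the printed percentages as PPV, f × printed / 0.45 gives 26.7, 33.3, 44.7, 54.2 and 64.4%, nearly the same sensitivities.

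**Step 4: test the Section 1.3 claim.** Sensitivity of 80% requires f ≥ 0.80 × 0.45 = 0.36. At the stated 15 to 30% the ceiling is 33 to 67%, whatever the effect size. Among 100 patients at f = 15% there are 15 carriers and 45 responders, so at most 15 of the 45 can be found. At the detectable difference, 15 × 0.79 ≈ 12 are found and about 33 of 45 (74%) are missed.

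**The case against.** The strongest reply is that Section 1.3 is not confined to single genes or to the rows of Table 3. The sensitivities above hold at the minimum detectable difference and are not upper limits. Section 1.1 says that close to half of patients carry a mutation in at least one of the four genes, Section 14.2.5 lists that pooled contrast as a subgroup, and Section 14.2.2 foresees combined groups. At f = 50%, sensitivity of 80% means response of 0.80 × 0.45 / 0.50 = 72% in carriers and 0.20 × 0.45 / 0.50 = 18% in non-carriers. That difference of 0.54 is about twice the 0.26 in Table 3, so power is close to 100%. Power to detect a group with 80% sensitivity stays at 80% or more for frequencies of about 36 to 65%. This stands. A reader might infer that the Section 1.3 sentence is false outright, but the documents support only that it does not follow from Table 3 and cannot hold for the individual named genes.

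A reader might also extend the criticism to the sentence that "a reasonable cut off would be if at least 30% of clinical response could be attributed to the presence of a specific mutation" and conclude that no row of Table 3 meets it. That depends on one reading of an ambiguous phrase. As a share of all responses (f·d/0.45) the rows give 13 to 29%; as a share of carriers' responses (d/p_c) they give 44 to 51%, and every row passes. Nor should the cut-off simply be rewritten as a 30-point difference: at alpha 0.05, Table 3 itself needs 0.40 and 0.35 at 15 and 20% frequency. The phrase is not evidence of the same error.

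Finally, the label does not enter the chi-square test, the sample size or the primary analysis. Actual sensitivity and PPV can be read from the planned contingency tables, and Section 5.1 does not expect exome results to direct treatment. This limits the consequences. It does not make the stated performance correct.

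**Conclusion.** The column is PPV under the wrong name. True sensitivity at the printed differences is about 26 to 64% across the table and 26 to 44% at the frequencies given for the named genes; the printed figure is about three times too high at 15% frequency (80 against 26%). The Section 1.3 claim is unsupported by Table 3 and impossible for a single gene mutated in 15 to 30% of patients. Even under the printed label, one row equals 80% and none exceeds it.

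This rests on three assumptions:
- Carrying the mutation is the positive test for response, as the column heading implies.
- Overall response is 45%. A lower rate raises the ceiling, but 80% becomes possible only if overall response is at most 0.30/0.80 = 37.5% for a gene at 30%, or 0.15/0.80 = 18.75% for one at 15%.
- The printed differences are kept. They do not give a uniform 80% power: an uncorrected two-sided chi-square approximation at 0.05 gives 86, 83, 80, 77 and 75%. The text example also uses a different level ("at a 2-sided 0.1 alpha error"). That is a separate matter, but the sensitivities will shift if the differences are revised.

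**What to change.** In the current protocol:

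1. Table 3: rename the last column PPV (response rate in carriers).
2. Table 3: add a sensitivity column computed as f·p_c/0.45 at the final detectable differences. At those now printed the entries are 26, 32, 44, 54 and 64%. Settle the differences and alpha before fixing these values.
3. Section 1.3: replace the sensitivity sentence with the PPV the study can detect, about 80% at 15% mutation frequency, falling to 58% at 50%. If a sensitivity of 80% is still wanted as an aim, tie it to a pooled or combined group with a frequency of at least 36%.

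The cost is wording and one table, with no new patients, data or analyses. The stated diagnostic performance becomes less favourable. This point gives no ground for changing the 30% cut-off sentence.

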
Genomic Predictors of Decitabine Response in AML/MDS

	
Treatment failure – Includes all patients who did not achieve a complete or partial remission.
 
Recurrence/morphologic relapse - Relapse following complete remission is defined as reappearance of blasts in the blood or the finding of $\geq 5\%$ blasts in the bone marrow, not attributable to any other cause. New dysplastic changes are considered a relapse. If there are no blasts in the peripheral blood and 5-20% blasts in the bone marrow, bone marrow biopsy should be repeated in > 1 week to confirm relapse.
 
Safety-- All patients receiving at least one dose of decitabine will be evaluated for safety.

Statistical considerations
	
This trial will be conducted as a phase II biomarker trial.
 
This trial is designed to detect the most clinically meaningful mutational predictors of response. These are mutations that have sufficient positive predictive value to be used as a clinical assay.
 
A power analysis was performed with Fisher’s exact test for mutation status and response to decitabine, assuming an expected 45% CR/CRi. With $\alpha = 0.05$, and a total anticipated enrollment of 100 evaluable patients, we anticipate 80% power to detect a 27% and 40% response difference between patients with and without a mutation, if the mutation occurs with a respective frequency of 30% and 15%. Such mutations would provide 80% sensitivity to predict response to decitabine. These are values that would warrant diagnostic clinical testing prior to therapy.
 
This trial is also designed to detect an improvement in clinical response compared to historical controls treated with 5 consecutive days of decitabine (20 mg/m²/day every 28 days)[2]. A power analysis was performed with Fisher’s exact test for response to decitabine compared to a historical rate of 24% observed in 55 patients. With 100 evaluable patients enrolled, we anticipate 90% power with $\alpha = 0.1$ to detect a 21% improvement in response (CR/ PR $\geq 45\%$). The reported CR/PR rate of the proposed treatment schedule (10 consecutive days of decitabine 20 mg/m²/day) is 64%[3]; the expected CR/PR rate of 45% is a conservative estimation of expected outcomes.

Study Schema:

Patients with progressive disease after two cycles (defined as a clear increase in bone marrow blast count, typically a > 50% increase in bone marrow blasts over baseline) should be removed from study.

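### The sensitivity column of Table 3 is the response rate in mutation carriers (PPV); true sensitivity is 26–64%, and the >80% claimed in Section 1.3 is out of reach for single genes at 15–30% frequency

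*Combined protocol and SAP*

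**What the plan says.** Section 14.2.2 introduces the design calculation with "A power analysis was performed using Chi-square test for the association between mutation and response to decitabine". Table 3, titled "Detectable mutation associated response rates (80% power", α = 0.05), is for 100 patients. It lists detectable differences in response rate of 0.40, 0.35, 0.30, 0.27 and 0.26 at mutation frequencies of 15, 20, 30, 40 and 50%. Its last column, "Sensitivity of mutation to predict response at minimum detectable response difference", gives 80, 75, 67, 61 and 58%. The footnote reads "Assuming the overall response rate (CR/CRi) of 45" per cent. The same section says that the named genes' "mutations in AML and MDS patients are each between 15% and 30% in multiple cohorts", and that the purpose is to find associations strong enough to justify testing before treatment.

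Section 1.3 turns the column into a design property: "This study is powered to identify mutations with >80% sensitivity to predict decitabine response if used as a clinical assay".

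The Study Synopsis of an earlier protocol version in the same file says of mutations at 30% and 15% frequency: "Such mutations would provide 80% sensitivity to predict response to decitabine". That text is superseded and is used here only as background. No section gives sensitivity a special definition.

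**The concern.** Sensitivity is the probability that a responder carries the mutation. PPV is the probability that a carrier responds. For a marker found in 15–30% of patients, when 45% respond, the two are far apart: a rare marker may pick out patients who nearly all respond and still miss most responders.

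The trend in the column is the first warning. At these differences true sensitivity should rise with mutation frequency, but the printed values fall.

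What is at stake is the reading of assay performance. Someone relying on Section 1.3 or Table 3 would expect a positive single-gene finding to capture most responders, and might treat a negative test as predicting non-response.

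**Working it through.** **Inputs** (Section 14.2.2 and Table 3): overall CR/CRi rate 0.45, mutation frequency f, and difference d in response rate, carriers minus wild-type.

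**Formulas.** From f × p_mut + (1 − f) × p_wt = 0.45 and p_mut − p_wt = d:

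- response rate in carriers (PPV): p_mut = 0.45 + (1 − f) × d
- response rate in wild-type: p_wt = 0.45 − f × d
- sensitivity: f × p_mut / 0.45
- ceiling on sensitivity, if every carrier responds: the smaller of 1 and f / 0.45

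**Example, 15% row.** p_mut = 0.45 + 0.85 × 0.40 = 0.79; p_wt = 0.45 − 0.15 × 0.40 = 0.39; sensitivity = 0.15 × 0.79 / 0.45 = 0.263; ceiling = 0.15 / 0.45 = 0.333.

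| f | d | Printed column | PPV | Wild-type response | True sensitivity | Ceiling |
|---|---|---|---|---|---|---|
| 15% | 0.40 | 80% | 79.0% | 39.0% | 26.3% | 33.3% |
| 20% | 0.35 | 75% | 73.0% | 38.0% | 32.4% | 44.4% |
| 30% | 0.30 | 67% | 66.0% | 36.0% | 44.0% | 66.7% |
| 40% | 0.27 | 61% | 61.2% | 34.2% | 54.4% | 88.9% |
| 50% | 0.26 | 58% | 58.0% | 32.0% | 64.4% | 100% |

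**Which quantity was printed?** PPV reproduces the column within 2 points in every row; sensitivity does so in none. Specificity (94, 90, 82, 72, 62%) and NPV (61, 62, 64, 66, 68%) do not fit. Nor does the sensitivity of wild-type status if the mutation marked resistance (96, 92, 84, 74, 64%).

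**Does rounding matter?** Taking the printed values as p_mut, each with its own implied overall rate, again gives sensitivities from 26% to 64%. The detectable differences are taken as printed. Recomputed chi-square minima (0.375, 0.340, 0.300, 0.282, 0.275) are all within 0.025 of them and would give sensitivities of 26, 32, 44, 55 and 65%.

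**What would 80% sensitivity need?** It needs f × p_mut = 0.80 × 0.45 = 0.36, so f must be at least 36%.

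- At f = 40%: p_mut = 0.36 / 0.40 = 0.90; p_wt = (0.45 − 0.36) / 0.60 = 0.15; difference 0.75.
- At f = 50%: p_mut = 0.36 / 0.50 = 0.72; p_wt = 0.09 / 0.50 = 0.18; difference 0.54.

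**Effect on power.** The column does not enter the power calculation. The worked example in the text, "100 patients will provide 80% power to detect 30% difference at a 2-sided 0.1 alpha error", taken at 20% frequency, gives 79.3% by the chi-square formula, so it reproduces.

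**The case against.** The strongest reply is that this is a label, and nothing in the analysis uses it. The sample size, chi-square or Fisher test, alpha and permutation correction are untouched. The primary objective (Section 2.1) is correlation with response, not assay validation. The cut-off proposed in Section 14.2.2, 30% of response attributable to a mutation, does not refer to the column. Section 5.1 does not expect the results to steer treatment directly. All of this stands, and it limits the point to a wrong statement of assay performance.

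Three stronger readings are tempting, and the documents do not support them.

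- **That more than 80% sensitivity is impossible for every planned marker.** Table 3 includes 40% and 50% rows, Section 1.1 puts the four genes together at nearly half of patients, and Section 14.2.5 plans that combined comparison. The ceiling there is 89–100%. Taken literally, Section 1.3 could describe such a marker, and one that strong would be detected almost certainly. But Section 1.3 speaks of mutations, Section 14.2.2 puts the named genes individually at 15–30%, and the tabled differences at 40–50% give only 54–64%.
- **That most responders are wild-type throughout the design.** This holds at 15–30% frequency (56–74% of responders at the tabled differences). In the 40% and 50% rows most responders are carriers, and in the 50% row the printed 58% is below the true 64%.
- **That the trial is underpowered or the wrong size.** Nothing in this point shows that.

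On versions: the file is the second of two parts, and a later text may exist. The Section 1.3 sentence and Table 3 are the same in every version that can be seen.

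**Conclusion.** The label is wrong, and so is the Section 1.3 claim for the single genes it names. At 15–30% frequency the printed values (80, 75, 67%) are 1.5 to 3 times the true sensitivity (26, 32, 44%). At the minimum detectable differences, a single-gene test would have a PPV of about 66–79% and miss 56–74% of responders, and 36–39% of wild-type patients would still respond.

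The size rests on the plan's 45% response rate and its 15–30% gene frequencies. At 30% frequency, 80% sensitivity becomes arithmetically possible only if overall response is 37.5% or lower (0.30 / 0.80) and every carrier responds. Counting PR as well, as Section 14.2.3 does for overall response, can only add responders, which lowers the ceiling.

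The earlier synopsis also gives adequate positive predictive value as the aim. That fits a mislabelled PPV rather than a faulty design.

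**What to change.** - In Table 3, relabel the last column *response rate in mutation carriers (PPV)* and add a true sensitivity column: 26, 32, 44, 54, 64%.
- In Section 1.3, replace the sentence with: *for single genes at 15–30% frequency, the minimum detectable differences correspond to a PPV of about 66–79% and a sensitivity of about 26–44%, assuming 45% overall response.*
- In Section 14.2.2, state that any case for pre-treatment testing will rest on both PPV and sensitivity, taken from the contingency tables already planned.

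The cost is protocol and SAP wording and a less favourable statement of assay performance. No new data are needed, and the sample size, test and detectable differences stay as they are for this point.

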14.2.3 Secondary Endpoint Analyses

The overall response rate (CR/CRi/PR) and complete response rate (CR/CRi) will be compared with historical controls[2], and the 95% confidence intervals will be provided.

The rate of patient specific mutation clearance after 10, 28, and 56 days of therapy will be determined using an Illumina based platform. We will compare the rate of mutation clearance between the patients who achieve a CR/CRi after 4 cycles and those who do not. We anticipate that we will identify between 6 and 25 exonic SNVs per case (the range obtained with >200 AML samples sequenced to date with whole genome or exome sequencing), and that the expected 95% confidence

interval of the mean variant allele frequency will be $\pm 2.56\%$ and $\pm 1.25\%$, respectively, if we assume an anticipated standard deviation of 3.2% within the same clone. The change of tumor burden over time and its association with clinical response will be assessed using 2-way ANOVA for repeated measurement data, followed by the ad-hoc multiple comparisons for between-group differences (e.g., responders vs. non-responders) at given time points as well as the between-time differences within each group. The resultant critical P values will also be corrected using permutation analysis for multiple testing.

The steady-state plasma decitabine concentration on day 4 ± 1 will be measured and correlated with clinical overall response.

The percent decrease in bone marrow methylcytosine will be calculated on day 10 ± 1 . We will compare this reduction with previously published data and between the patients who achieve CR/CRi and those who do not. The correlation of peak plasma levels of decitabine with response will be assessed using 2-sample t-test or Mann-Whitney non-parametric rank-sum test as appropriate. The change of total bone marrow DNA methylcytosine from baseline and its association with both steady-state plasma drug levels and response will be assessed using 2-way ANOVA for repeated measurement data, followed by the ad-hoc multiple comparisons for between-group differences (e.g., responders vs. non-responders) and between-time differences. Similar analyses will be performed for the correlation of expression profiles and SNP analysis with pharmacokinetic data.

Statistical power justification. A power analysis was performed using two-sample t-test for between-group difference and paired t-test for the change over time. For tumor clearance, this will provide $> 99\%$ power to detect a 10% difference in the means at two separate time points for clones with 6 or more variants, and $> 98\%$ power to detect a 15% difference if there are 3 or more variants per clone with $\alpha = 0.05$ (power will decrease to 91% and 82%, respectively, in cases where the standard deviation is 4.7%, the maximum we have observed thus far). For pharmacologic correlations, we anticipate 85% power to determine a 25 ng/ml difference between the average C_{\max} of 45 evaluable responders and 55 evaluable non-responders with an anticipated average C_{\max} of 70 ng/ml and a standard deviation of 40 ng/ml within the entire cohort, and with $\alpha = 0.05$. [22] We believe a less significant difference would not be sufficient to warrant application in clinical decision making (i.e. whether to continue therapy for more than 1 cycle). We anticipate 99% power to determine a difference of 20% in the reduction of bone marrow methylcytosine between 45 evaluable responders and 55 evaluable non-responders with an expected standard deviation of 15% and $\alpha = 0.05$. [28, 66-68] The difference in methylcytosine reduction previously observed was 30% between patients achieving CR/PR and those with only hematologic improvement. [28]

Time to relapse and time to death will also be listed for each patient.

